8.5. SPONSOR	14
8.6. FUNDING	14
8.7. AUDITS	15
9. STUDY MANAGEMENT	15
10. PUBLICATION POLICY	15
11. REFERENCES	15

GLOSSARY OF ABBREVIATIONS

CIV	Common iliac vein
MTS	May Thurner Syndrome
DVT	Deep vein thrombosis
IVUS	Intravascular Ultrasound
CFV	Common femoral vein

KEYWORDS

Common Iliac Vein (CIV) May-Thurner Syndrome (MTS) Duplex Ultrasound

STUDY SUMMARY

TITLE The use and reproducibility of duplex ultrasound to provide indices of left Common Iliac Vein (CIV) diameter, for improved diagnosis of May Thurner Syndrome (MTS) in patients presenting with unexplained left leg swelling.

DESIGN Feasibility/Pilot Study.

AIMS To investigate the use and reproducibility of duplex ultrasound to determine diameter indices of left CIV compression.

OUTCOME MEASURES The diameter measurement of the left CIV in adults, and the inter- and intra-operator variation of the diameter measurement of the left CIV using duplex ultrasound.

POPULATION Adult patients referred to the vascular ultrasound department.

ELIGIBILITY Patients with or without venous disease, who have not had previous treatment for iliac vein disease.

DURATION 9 months

REFERENCE DIAGRAM

[if appropriate]

1. INTRODUCTION

1.1. BACKGROUND

May Thurner Syndrome (MTS) is a vascular condition whereby the left common iliac vein (CIV) becomes compressed between the right common iliac artery and the spine. This condition is often asymptomatic, however MTS can cause severe left lower limb complications such as swelling, pain, oedema, reflux, varices, skin changes and deep vein thrombosis (DVT). It is thought that approximately 2-3% of lower limb DVT's are caused by MTS, however there is an almost 56% predominance for left sided DVT suggesting this number is underestimated and cases of MTS are regularly missed (Peters et al., 2012). DVT can be a serious medical condition and can go on to cause pulmonary embolism, a sometimes fatal condition if not identified and treated quickly and effectively.

Diagnostic imaging studies such as ultrasonography, venography and intravascular ultrasound (IVUS) are used to evaluate the CIV and identify the site and severity of any narrowing that is present. Duplex ultrasound is often the first line of imaging as it is risk free, cost effective, and accurate at identifying lower limb venous insufficiency. However the location of the iliac veins deep in the abdomen has limited its use for identifying specific features of MTS. It is also highly operator dependent and the results obtained may be dependent on the experience level of the vascular scientist performing the scan. Abdominal ultrasound scans are also always performed with the patient lying completely flat, however this does not reflect the haemodynamic changes that occur within the venous system when a patient is standing. Indirect measurements can be taken to help indicate if there is an iliac vein obstruction, such as interrogation of the common femoral vein (CFV) to assess phasicity and reflux. However, these readings can suggest proximal problems but do not differentiate between compression and thrombus.

The gold standard for diagnosing MTS is venography, whereby a catheter is inserted into the iliac system and changes in pressure gradients are calculated across the region of compression. This procedure, however, is invasive, time consuming and exposes patients to radiation and contrast dyes. IVUS is also a well-used diagnostic tool for MTS. It is highly sensitive at identifying CIV compression and the development of intraluminal "spurs" and neointimal hyperplasia that is associated with MTS. IVUS however is also invasive, is unable to provide information related to extravascular lesions and there are fewer studies that have looked into the use of IVUS and the benefit to patient outcomes.

Metzger et al. (2016) examined the suitability of using velocity ratios to determine CIV stenosis. They used ultrasound to examine 76 patients with a range of chronic venous insufficiency symptoms. They took velocity measurements before an area of obstruction and within it, to create a venous iliac velocity ratio (VR). All patients were also assessed using IVUS, and diameter and area reduction measurements were recorded. Results found that a VR of >2 equated to a significant iliac lesion (defined as $>50\%$). The results of this research are consistent with the case study by Oğuzkurt et al. (2007), who found an increase in velocity from 40cm/s to 100cm/s in the left CIV. This would equate to a VR of 2.5, and therefore a $>50\%$ obstruction on IVUS. The use of velocities to examine iliac veins, however, is controversial as peak systolic velocity measurements originated from arteries, where a critical stenosis is defined as $>75\%$ reduction in the diameter of the artery (Sloves and Almeida, 2018). Applying the same method to veins is difficult, as veins differ in shape and size, particularly those that are diseased or compressed as they become more elliptical in shape. Also, it is venous pressure rather than venous flow that plays the key role in venous stenosis. Additionally, all patients in this study were required to fast for 6 hours prior to having the ultrasound scan and were administered with dimethicone to aid visualisation of the iliac vessels. This is therefore not an accurate representation of the kind of scans that take place on a day to day basis, with few patients asked to fast before coming to a hospital appointment and none given medication to aid the process. Although in this study the VR was comparable to IVUS, it may not be reproducible in a workplace setting.

Another study used ultrasound to interrogate the CFV as a means of determining a value for identifying iliac vein stenosis. Mousa et al. (2016) examined the CFV and saphenofemoral junction in 36 patients with chronic venous ulcers, to see if reflux in the CFV (described as persistent reverse

flow for more than 1.0 second demonstrated on the Doppler spectral display) can be used to determine iliac vein stenosis greater than 50% (which was quantified using IVUS). They found that reflux in the CFV of greater than 2.5 seconds correlated to an iliac vein stenosis of greater than 50% (Mousa et al., 2016). This finding may be of great importance for deciding on effective treatment strategies for patients with chronic venous ulcers, such as the potential for iliac vein stenting when reflux is found to be greater than 2.5 seconds in the ipsilateral CFV. However, these measurements may not directly correspond to iliac vein compression and MTS, and further evaluation of these two parameters would be needed.

Similar research by Hui et al. (2020) looked at the use of lower extremity ultrasound as a screening tool for detecting ilio caval obstruction. The retrospective study examined images from 132 patients who had undergone lower extremity venous procedures over a 22 year period. Images from CT, MR and conventional venography were compared to the spectral Doppler image taken from the CFV on the same patient. The investigators examined phasicity and response to the Valsalva manoeuvre as a predictor of iliac vein patency. The study found that overall sensitivity of using nonphasic flow or response to Valsalva manoeuvre as an indicator of ilio caval obstruction was poor, whereas the specificity was reasonably good. It was suggested from this that positive results are likely to indicate a true obstruction in the ipsilateral iliac system, whereas negative results may not be reliable and the usefulness of these results may be questionable (Hui et al., 2020). Relating this to MTS, interrogation of the flow patterns in the CFV could indicate a complete compression of the CIV, but could not be used to indicate the degree of compression or used as a diagnosis tool. Therefore further research is required in this area to determine if duplex ultrasound can be used to directly image CIV compression, and if it can be used to determine a specific diameter measurement at which the CIV is considered compressed or not compressed.

1.2. RATIONALE FOR CURRENT STUDY

More widespread use of ultrasound for examining the iliac veins would be beneficial as it may avoid the need to expose patients to the invasive procedures requiring radiation and contrast agents that are necessary for venography and IVUS. Previous studies examining duplex ultrasound and iliac veins, as mentioned above, have examined the use of velocity ratios, interrogation of the CFV and examination of phasicity but have not investigated using ultrasound to measure the absolute diameter of the CIV. There is currently no definitive diameter that the CIV can be considered compressed or not compressed. All of the previous studies used symptomatic patients only and so it cannot be assumed that the results would correlate in asymptomatic patients. Also, it is known that ultrasound is highly operator dependent but none of the previous studies examined the impact of this on measuring the CIV diameter. Therefore, further work needs to be carried out to assess the use of ultrasound for imaging the left CIV and aiding MTS diagnosis.

The principle research question is whether duplex ultrasound could be used to image the left CIV and investigate diameter ranges that can help in the diagnosis of MTS. The first objective is to use duplex ultrasound to image the left CIV in a cohort of patients referred to the vascular ultrasound clinic. The second objective is to determine inter- and intra-observer variation of the diameter measurement of the left CIV using duplex ultrasound. The hypothesis is that ultrasound can be used to image left CIV compression and the measurements obtained during the examination are highly reproducible both within an operator and between operators.

If the results of this research study find that ultrasound can be used to image the left CIV, can define 'normal' diameter ranges and is a reproducible diagnostic tool, then this could reduce the time taken for patients presenting with symptoms of MTS to be diagnosed. Ultrasound is a quick and readily available imaging tool, and so creating an appropriate scanning protocol will enable regular scanning and screening of patients who may have this condition. As well as aiding diagnosis it should also help reduce the number of patients with this condition that go on to suffer from further severe complications such as DVT. These results should also help identify which patients need to go on to have the more invasive tests and rule out patients that do not require them. Iliac vein scanning with ultrasound is not routinely performed in all vascular departments across the country, with many only taking indirect measurements from the CFV's. If a benefit is found to doing this scan then it could be introduced to many more/all departments, benefiting many more patients.

2. STUDY OBJECTIVES

The primary objective of this study is to investigate diameter variation of the left CIV based on posture in adults referred to the vascular ultrasound department, using duplex ultrasound.

The secondary objective of this study is to determine inter- and intra-observer variation of the diameter measurement of the left CIV using duplex ultrasound, in adults referred to the vascular ultrasound department.

3. STUDY DESIGN

The study will be a feasibility/pilot study lasting approximately six months, recruiting 40 patients from the vascular ultrasound department at Imperial College Healthcare NHS Trust. 20 patients will be symptomatic for lower limb venous disease and 20 patients will be asymptomatic. The following outlines the timeline of events for the patients recruited onto the study.

OUTPATIENT APPOINTMENT

At their outpatient appointment patients who may be eligible to take part in the study will be identified and approached. Patient notes and GP referral letters will be read prior to seeing the patient in the outpatient appointment, to identify suitable participants. Suitable participants will be those that will be requiring a vascular ultrasound scan in the vascular ultrasound department. The study will be explained and if the patient gives verbal consent to receiving study information material, then this will be given to the patient for consideration. They will be told that formal consent will be taken at their scan appointment if they agree to partake in the study and that if they choose not to partake this will not affect their usual clinical care. Participants will be given up to six weeks to decide if they would like to take part.

TELEPHONE CALL

Patients will be contacted two weeks after their outpatient appointment to enquire as to whether they would like to take part in the study. Those that decline will have their scan request form passed on to the department receptionist for booking in the usual way. Those that would like to take part in the study will have a date and time arranged to come to the department to have their scan as part of the study, followed by the scan requested by the clinical team. The study scan and the routine scan will be made on the same day to avoid the patient having to come to the hospital multiple times. Some patients from the symptomatic group may have been referred for this type of scan.

[figure not shown]
ULTRASOUND SCAN APPOINTMENT

Order of events at the scan appointment will be as follows;

[figure not shown]
- Eligibility check and formal consent - 5 minutes
- Recording of demographic details and medical history - 5 minutes
- The patient will have their routine scan performed as requested by the referring clinician - Between 30 and 90 minutes, dependent on the scan type requested.
- A clinical vascular scientist will perform the study ultrasound scan and take three readings of the left CIV with the patient lying flat and three readings of the left CIV with the patient at a 45 degree angle on a tilted examination couch - 10 minutes
- Two further clinical vascular scientists will perform the same study scan and take the same readings - 20 minutes
- Patient will be thanked for their time and a routine follow up appointment will be made with the referring clinician.

The below flow chart illustrates this order of procedures:

Prior to the ultrasound scan appointment:

During the ultrasound scan appointment:

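### Only the left common iliac vein is measured, but the symptomatic group has no leg side: record side and pre-specify a left-or-bilateral comparison beside the planned one

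*Combined protocol and SAP*

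**What the plan says.** The title in the Study Summary gives the purpose as indices of left CIV diameter "for improved diagnosis of May Thurner Syndrome (MTS) in patients presenting with unexplained left leg swelling". Section 1.1 describes May-Thurner Syndrome (MTS) as a left-sided problem: "MTS can cause severe left lower limb complications". At the scan appointment (Section 3), each of three scientists takes three readings lying flat and three at 45 degrees, all of the left CIV.

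Side does not appear in the group definition. Section 3 says only that "20 patients will be symptomatic for lower limb venous disease and 20 patients will be asymptomatic", and adds that some of the symptomatic patients may have been referred for this type of scan. The eligibility line of the Study Summary reads "Patients with or without venous disease, who have not had previous treatment for iliac vein disease". Sections 4.2 and 4.3 require a vascular ultrasound scan and have no criterion on side.

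Section 7 plans a one-way ANCOVA of iliac vein diameter between the two groups. It does not say how the side of symptoms enters. Demographic details and medical history are recorded at the scan appointment. The case report form is not among the documents, so side may already be captured; what is missing is a stated use of it.

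**The concern.** The vein measured belongs to one side, while the label that sorts patients belongs to either. A patient whose symptoms are confined to the right leg enters the ANCOVA as symptomatic, although the vein under study does not drain the symptomatic leg.

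Two things are at stake. The expected difference between groups may be diluted. The diameter range reported for symptomatic patients may also be harder to interpret, and that range bears on the research question in Section 1.2, to "investigate diameter ranges that can help in the diagnosis of MTS", and on the hope there that "These results should also help identify which patients need to go on to have the more invasive tests". With 20 patients per group, a handful of right-only patients is a visible fraction. If their handling is settled only after the diameters are known, an avoidable analytic choice stays open.

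**Working it through.** **The plan's own figure.** Section 7 uses a prevalence of 2%, 95% confidence and a 5% margin: n = 1.96² × 0.02 × 0.98 / 0.05² = 30.12, rounded up to 31. This reproduces. It is a precision calculation for one proportion. It does not depend on leg side and gives no power for the group comparison.

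**Inputs.** From Section 3: 20 symptomatic and 20 asymptomatic patients. Not in the documents, so assumed: the number of right-only patients (4 of 20, for illustration), the size of any shift in left CIV diameter (in SD units), equal SDs, two-sided alpha 0.05, no covariate. The asymptomatic group and, except in the third power scenario, the right-only patients are taken as unshifted.

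**Dilution.** If a fraction q of the symptomatic group has no shift and the rest have mean shift d, the expected group difference is (1 − q) × d. With q = 4/20 = 0.20 this is 0.80d, so 20% smaller.

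**Precision.** 95% CI half-width in SD units:

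- 20 v 20: t(38) × √(1/20 + 1/20) = 2.024 × 0.316 = 0.640
- 16 v 20: t(34) × √(1/16 + 1/20) = 2.032 × 0.335 = 0.682

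**Power** (t-test, by noncentral t and simulation), right-only patients left in (20 v 20) against left out (16 v 20). A difference of 0.91 SD is what 20 v 20 detects with 80% power.

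| Scenario | Left in | Left out |
|---|---|---|
| All left/bilateral patients shifted 0.5 SD, right-only unshifted | 23% | 30% |
| Same, 0.91 SD | 58% | 75% |
| 3% of left/bilateral patients shifted, by 1 to 3 SD | about 5% | 5–6% |
| 10% shifted, by 1 to 3 SD | 6–9% | 6–11% |
| 25% shifted, by 2 SD | 18% | 24% |
| Right-only patients carry the full shift, 0.5 SD | 34% | 30% |
| Same, 0.91 SD | 80% | 75% |

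**Break-even.** Let right-only patients carry a fraction f of the left-leg shift. Left in, the expected difference is [1 − 0.2(1 − f)] × d with half-width 0.640; left out, it is d with half-width 0.682. The two are about equally informative when 1 − 0.2(1 − f) = 0.640/0.682 = 0.94, so f is about 0.7. Below that, the side-specific comparison has more power; above it, the all-symptomatic one does.

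**The case against.** The strongest reply is that the comparison is peripheral and the broad group may be intended. The primary objective in Section 2 is to "investigate diameter variation of the left CIV based on posture in adults referred to the vascular ultrasound department"; the secondary is observer variation. Both use every left CIV reading whichever leg has symptoms, and the outcomes in Section 3.1 list no group difference. Section 1.2 faults earlier work for studying symptomatic patients only, so a plain symptomatic-versus-asymptomatic contrast fits the rationale. This stands, and it keeps the weight low.

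Nor is it shown that right-only patients have normal left CIVs. Section 1.1 says of MTS that "This condition is often asymptomatic", so they may also have compression, as may the asymptomatic group. This stands too. A reader might infer that right-only patients should be removed and the side-specific comparison should replace the planned one. The documents do not support that: above about 70% of the left-leg shift, removal loses power.

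A reader might also infer a large loss of power from the 58% v 75% line. That line needs every left-leg or bilateral patient to be shifted by 0.91 SD. Section 1.1 puts MTS at about 2–3% of lower-limb DVTs, a figure it thinks too low and which does not describe this study's patients. With shares of 3% or 10%, leaving right-only patients out changes little.

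Finally, Section 7 has other gaps, such as unnamed covariates and no stated posture for the comparison. That is true, but those are missing details. Here the plan, followed as written, pools patients whose symptoms lie in a leg that the measured vein does not drain.

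**Conclusion.** The gap is real and the point is one to consider, at low weight. The group definition, the eligibility criteria and Section 7 all leave out side, so right-leg-only patients count as symptomatic in a comparison of left CIV diameter.

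The expected difference falls by their share of the group if they carry no shift, and by less if they carry some. The actual size cannot be given, because the right-only share, the shift and the SD are not in the documents; the figure of 4 in 20 is an illustration. Dilution from left-leg disease not caused by MTS remains whatever is done about side, and may be the larger problem.

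**What to change.** Make sure side of symptoms (left, right, both, none) is captured with the medical history already recorded at the scan appointment. In Section 7:

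- keep the planned all-symptomatic versus asymptomatic comparison;
- pre-specify beside it a comparison of patients with left-leg or bilateral symptoms versus patients with no symptoms in either leg;
- describe diameter ranges for right-only patients separately;
- keep all patients in the posture and reliability analyses.

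The cost is one or two sentences in Section 7 and one data item if side is not already on the case report form. No scan, staff time or patient is added. The downside is one extra analysis, with a smaller symptomatic group and so the wider interval shown above; presenting it beside the planned comparison means that nothing is lost if right-only patients share the shift.

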4.2. INCLUSION CRITERIA

Patients will only be included if:

- They have the capacity to consent.
- They are required to have a vascular ultrasound scan in the vascular ultrasound department at ICHT.

THEY ARE 18 YEARS OF AGE OR OLDER AT THE START OF THE STUDY.

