4.3. EXCLUSION CRITERIA

Patients will be excluded if:

- They do not have capacity to consent.
- They do not require a vascular ultrasound scan as part of their routine care.
- They are under 18 years of age at the start of the study.
- They are pregnant.
- They have had previous interventions/treatment for iliac vein disease.
- They have had a previous diagnosis of iliac vein thrombus.

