7. STATISTICS AND DATA ANALYSIS

The sample size has been calculated using a sample size calculator assuming a prevalence of 2%, confidence level of 95% and margin of error of 5%. This calculation gives a sample size of 31. This sample size is in line with a previous study by Mousa et al. (2016) which had a sample size of 36.

A one-way ancova test will be performed to assess the difference in iliac vein diameter between the two groups. An intraclass correlation coefficient will be used to measure intra- and inter-observer reliability. Support will be provided from the Imperial Statistics Services during the analysis phase.

Statistics and data analysis aspects of the study have been reviewed by [name], the academic supervisor at Manchester Metropolitan University.

Data and all appropriate documentation will be stored for a minimum of 10 years after the completion of the study, including the follow-up period.

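### The title, principal question and hypothesis concern MTS diagnosis and imaging of left CIV compression, but no entry rule or study procedure ensures that compressed veins are enrolled or identified

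*Combined protocol and SAP*

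**What the plan says.** - **Target.** The title in the Study Summary describes diameter indices "for improved diagnosis of May Thurner Syndrome (MTS) in patients presenting with unexplained left leg swelling". The aim line below it also refers to indices of compression. In Section 1.2 the principal question is about diameter ranges that help diagnose MTS, and the hypothesis reads: "The hypothesis is that ultrasound can be used to image left CIV compression and the measurements obtained during the examination are highly reproducible". The last paragraph of Section 1.2 expects results that help decide who needs invasive tests and who does not.
- **Entry.** Besides adult age and capacity, Section 4.2 asks only that "They are required to have a vascular ultrasound scan in the vascular ultrasound department at ICHT". Section 3 sets the split: "20 patients will be symptomatic for lower limb venous disease and 20 patients will be asymptomatic". The Study Summary admits patients with or without venous disease. Section 4.3 removes patients with a previous iliac vein thrombus and those of whom it is true that "They have had previous interventions/treatment for iliac vein disease". Section 3 notes that some symptomatic patients may have been referred for this type of scan, but gives no number and no priority.
- **Objectives and outcomes.** Section 2 has posture-related variation in left CIV diameter as primary and observer variation as secondary, both in adults referred to the department. Section 3.1 lists matching outcomes.
- **Sample size.** Section 7 gets 31 patients by "assuming a prevalence of 2%, confidence level of 95% and margin of error of 5" (percent). It does not say what condition the 2% refers to.

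**The concern.** The question asked and the patients recruited are different. Twenty patients with varicose veins would fill the symptomatic half without breaking any rule, and none need have a swollen left leg or a compressed iliac vein. With few or no compressed veins, the study could not show that compression can be imaged, and it could not give a diameter that separates compressed from uncompressed veins.

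Reproducibility is affected too. Section 1.1 says that compressed veins become more elliptical and gives this as a reason why measurement methods are hard to transfer to them. A high intraclass correlation obtained mostly in uncompressed veins need not hold in the veins of diagnostic interest, yet under the present title and hypothesis it could be read as support for an MTS diagnostic tool.

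**Working it through.** **1. Target set against entry rules**

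| Element | Needed for the title and hypothesis | What the plan provides |
|---|---|---|
| Symptom | Unexplained left leg swelling | Lower limb venous symptoms of any cause in half the patients (Section 3) |
| Referral | Suspected MTS or iliac compression | Any vascular scan (Section 4.2); iliac scan referrals possible, number not given (Section 3) |
| Confirmation | A way to label a vein compressed or not | No venography or IVUS among the study procedures (Section 3); no follow-up (Section 6); no accepted diameter threshold (Section 1.2) |

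The third row matters as much as the first two. Even if compressed veins are enrolled, no study procedure identifies them independently of the diameter under study.

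**2. The plan's own figure**

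Inputs from Section 7: p = 0.02, d = 0.05, 95% confidence (two-sided, z = 1.96).

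n = z² p(1 − p) / d² = 1.96² × 0.02 × 0.98 / 0.05² = 30.12, rounded up to 31. This reproduces the stated 31. The one-sided version gives 22 and does not match.

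**3. Illustration: how many MTS cases if 2% were the rate**

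Expected cases = n × p. P(none) = (1 − p)^n. P(at most one) = (1 − p)^n + n p (1 − p)^(n − 1).

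- All 40 patients at 2%: 40 × 0.02 = 0.8 expected; 0.98^40 = 44.6% chance of none; 0.446 + 0.8 × 0.98^39 = 0.446 + 0.364 = 81% chance of at most one.
- The 20 symptomatic patients at 2%: 0.4 expected; 0.98^20 = 66.8% chance of none; 0.668 + 0.4 × 0.98^19 = 0.668 + 0.272 = 94% chance of at most one.

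**4. Range**

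| Rate | Expected in 20 | P(none in 20) | Expected in 40 | P(none in 40) |
|---|---|---|---|---|
| 2% | 0.4 | 66.8% | 0.8 | 44.6% |
| 3% | 0.6 | 54.4% | 1.2 | 29.6% |
| 5% (assumed) | 1.0 | 35.8% | 2.0 | 12.9% |
| 10% (assumed) | 2.0 | 12.2% | 4.0 | 1.5% |
| 20% (assumed) | 4.0 | 1.2% | 8.0 | <0.1% |

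None is more likely than at least one only below a rate of 1 − 0.5^(1/40) = 1.72% for 40 patients, or 1 − 0.5^(1/20) = 3.41% for 20.

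**5. What these numbers can bear**

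The only comparable figure in the documents is the 2–3% in Section 1.1. That is the share of lower limb DVTs caused by MTS, and the same sentence suggests it is an underestimate. It is not a prevalence among vascular referrals. It is also not a rate of compression, which Section 1.1 says often causes no symptoms. The table shows how sensitive the case count is to the rate; it does not estimate this study's case count.

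**The case against.** The strongest reply is that the formal objectives already fit the design. Neither the posture objective nor the observer objective in Section 2 needs an MTS case, the outcomes in Section 3.1 match, and the study is labelled feasibility/pilot. Broad entry also has a stated purpose: Section 1.2 faults earlier work for using symptomatic patients only. All of this stands. It limits the defect to the title, aim line, principal question, hypothesis and the benefits claimed in Section 1.2. It does not remove the defect, because those statements set how the results will be read.

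A reader might go further and infer that the study will probably contain no MTS case. The documents do not support that. At 2% over all 40 patients, at least one case is slightly more likely than none (55.4% against 44.6%). The 66.8% applies only to the symptomatic half. The 2% is itself undefined, and its likely source is a share of DVTs.

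Nor can one infer that hardly any compressed veins will be enrolled. Compression may be commoner than MTS, iliac scan referrals could raise the rate, and the iliac exclusions could lower it. The documents quantify none of these. Unlabelled compression would still not rescue the diagnostic aim, since nothing in the study would identify it as compression.

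**Conclusion.** The mismatch is documented and should be corrected. The plan can deliver left CIV diameters by posture and observer reproducibility in adults referred for vascular ultrasound. As written, it cannot support a diameter range for diagnosing MTS or a claim about who may be spared invasive tests.

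That conclusion rests on the entry rules and on the absence of any confirmation of compression, not on a prevalence. The case counts illustrate it under one assumption, that 2% is the MTS rate among those recruited. Even in the favourable outcome of a single case, no diameter range could be derived. At higher assumed rates more cases would be enrolled, but they would remain unconfirmed by any study procedure.

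**What to change.** **Main change (wording only).**
- Align the title, aim line, principal question and hypothesis with Sections 2 and 3.1: left CIV diameter by posture, and inter- and intra-observer reproducibility, in adults referred for vascular ultrasound.
- State in Section 7 that reproducibility applies only to the range of diameters observed.
- State that no MTS diagnostic range and no rule-out claim will be concluded, and amend the expected benefits in Section 1.2 to agree.

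**Optional change (recruitment order, total still 40).** Until a pre-set date in the recruitment period, give priority for the 20 symptomatic places to eligible patients referred for unexplained left leg swelling or an iliac vein scan. After that date, open the remaining places to other venous referrals. Report how many priority patients were enrolled.

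**Cost.** A protocol amendment, with no extra patients or procedures. Notes and referral letters are already read to find participants (Section 3), so the priority rule adds little work. The downsides are a narrower stated ambition and possibly slower recruitment of the symptomatic half. The yield of the priority rule is unknown, and it does not replace the wording change because compression would still be unconfirmed.
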